### **8.6.3 Laboratory Data**

Laboratory data will be summarized by treatment arm. Values outside the normal ranges will be summarized by treatment arm. In addition, selected laboratory data will be summarized by treatment arm and NCI CTCAE v4.3 grade.

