8.0 INCLUSION/ EXCLUSION CRITERIA

8.1 Inclusion Criteria

1. Informed Consent

- a. Ability to provide written informed consent in accordance with federal, local, and institutional guidelines

2. Target Population

- a. Age \geq 18 years
- b. Karnofsky Performance Score (KPS) \geq 70% ([Attachment 4](#))
- c. Estimated Life Expectancy of at least 3 mo
- d. Documented histological or cytological diagnosis of renal cell carcinoma with a clear-cell component.
- e. Measurable Disease per RECIST 1.1 as determined by the Investigator (see [Attachment 5](#))
- f. Must have received at least two prior lines of systemic therapy, including at least one VEGFR-targeting TKI (e.g., sunitinib, sorafenib, pazopanib, cabozantinib)
 - Radiographic progression of mRCC must have occurred (per investigator assessment) on or after the most recent systemic therapy and within 6 mo prior to C1D1.
- g. Prior treatment with other anti-cancer therapies including cytokines, monoclonal antibodies, immunotherapies, and cytotoxic chemotherapy is allowed (except for mTOR inhibitors, see Exclusion Criterion #1).

3. Laboratory Findings

- a. Serum creatinine \leq 2.0 \times upper limit of normal or calculated creatinine clearance \geq 30 mL/min (\geq 0.5 mL/sec) using the Cockcroft-Gault equation:
$$C_{Cr} = \{((140 - \text{age}) \times \text{actual body weight}) / (72 \times S_{Cr})\} \times 0.85 \text{ (if female)}$$
- b. Adequate hematological function, defined as ANC \geq 1,500/mm³, Hb \geq 9.0 g/dL, and platelet count \geq 100,000/mm³. Transfusions and growth factors must not be used within 2 weeks prior to randomization to meet these requirements.
- c. Alanine aminotransferase (ALT) and aspartate aminotransferase (AST) $<$ 3.0 \times upper limit of normal.
- d. Total bilirubin \leq 1.5 \times the upper limit of normal. For patients with Gilbert's disease, \leq 3 mg/dL (\leq 51.3 μ mol/L).
- e. HbA1c \leq 8%
- f. Fasting serum triglycerides \leq 2.5 \times upper limit of normal AND total cholesterol \leq 300 mg/dL (\leq 7.75 mmol/L). Lipid-lowering medication is allowed.

4. Reproductive Status

- a. Female patients of childbearing potential must have a negative serum or urine pregnancy test within 3 days prior to the first dose of study drug and agree to use dual

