ATTACHMENT 3: MSKCC PROGNOSTIC SCORE

Worksheet for Determination of Prognostic Score in Previously Treated Patients

Enter the patient’s assessment value in the Patient Value Column. If the patient value meets the criteria then enter “1”. To obtain the patient’s prognostic score, add up all the “1” entered in last column. The patient’s risk group is defined in the table below using the patient’s MSKCC prognostic score.

Parameter	Risk Factor	Criteria Value	Patient Value	If Patient Value meets criteria, enter 1
KPS	Low PS	< 80%		
Corrected Calcium*	High Corrected Calcium	≥ 10 mg/ dL		
Hemoglobin	Low Hemoglobin	Males: ≤ 13 g/dL Females: ≤ 11.5 g/dL		
Sum total= MSKCC Prognostic Score:				

*Corrected Calcium = ([4 – serum albumin in g/ dL] x 0.8 + serum calcium)

Risk Group Based on MSKCC Prognostic Score

Risk Group	MSKCC Prognostic Score
Favorable- Risk	0
Intermediate- Risk	1
Poor- Risk	2 or 3

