### **6.1.3 Safety Endpoints**

The safety endpoints are:

- Type, incidence, seriousness, nature, severity, and drug-relatedness of adverse events graded according to the National Cancer Institute Common Terminology Criteria for Adverse Events, Version 4.0 (NCI CTCAE v4.0)
- Changes in vital signs, physical findings, and clinical laboratory test results and following study treatment administration

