### 8.3 Analysis of Treatment Group Comparability

Demographic and baseline characteristics, including age, sex, race, ethnicity, baseline medical history, prior medications, disease characteristics, histology subtype, current disease status, and stratification factors will be summarized by treatment arm and overall subjects combined for the ITT and safety populations.

Baseline values are defined as the last available data obtained prior to the patient receiving the first dose of any study treatments on Cycle 1 Day 1 visits unless otherwise noted.

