### **8.6.2 Adverse Events**

Verbatim description of AEs will be mapped to Medical Dictionary for Regulatory Activities (MedDRA, v19.1) preferred terms and system organ classes, and graded by the investigator according to NCI CTCAE v4.03. Treatment-emergent adverse events (TEAEs) will be summarized by mapped term, appropriate thesaurus level, NCI CTCAE grade, and treatment arm. In addition, serious adverse events, severe adverse events (Grade  $\geq 3$ ), and adverse events leading to study drug discontinuation or interruption will be summarized accordingly. Multiple occurrences of the same event will be counted once at the maximum grade. All deaths are reported as SAEs per study conduct. In order to accurately summarize the true SAE rate, all SAE summaries will not count grade 5 events for patients who died due to progressive disease.

For reporting purposes, “treatment emergent” is defined as adverse events occurring on or after the first dose of study drug is administered until the clinical cutoff date, or existing events that worsened after the first dose during the study.

All listings of adverse events will also include all adverse events.

Deaths reported during the study treatment period and the follow-up period after treatment completion and/or discontinuation will be listed by treatment arm.

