### **8.6.4 Vital Signs**

Changes in selected vital signs will be summarized by treatment arm and by change over time, which includes change from baseline at each visit where parameters are scheduled to be collected. Baseline is defined as the measurement obtained on Cycle 1, Day 1 before the first dose of study drug is administered.

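### The SAP's laboratory tables have no baseline reference, so they do not deliver the stated endpoint of change and cannot separate abnormalities present at entry from new ones

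*SAP*

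**What the plan says.** SAP 6.1.3 lists as a safety endpoint "Changes in vital signs, physical findings, and clinical laboratory test results and following study treatment administration". SAP 8.6.3 (7.6.3 in the SAP's table of contents) is the matching analysis section and has three sentences. The first calls for a summary by arm. The second reads "Values outside the normal ranges will be summarized by treatment arm". The third says that "selected laboratory data will be summarized by treatment arm and NCI CTCAE v4.3 grade". None mentions baseline, change, shift, worst value after first dose, or restriction to values that worsened. Nor does the section say whether values or patients are counted.

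The next section, SAP 8.6.4, does specify this for vital signs: the summary is over time, "which includes change from baseline at each visit where parameters are scheduled to be collected". SAP 8.3 gives a general definition: "Baseline values are defined as the last available data obtained prior to the patient receiving the first dose of any study treatments". SAP 8.6.2 treats a pre-existing adverse event as treatment-emergent only if it is among "existing events that worsened after the first dose during the study". Protocol 14.4 describes the safety analysis in terms of adverse events only, so it does not supply the missing laboratory rule.

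Protocol 8.1 admits patients with creatinine up to 2.0 x ULN (or higher if the clearance criterion is met), ALT and AST just under 3.0 x ULN, bilirubin up to 1.5 x ULN, fasting triglycerides up to 2.5 x ULN, and hemoglobin from 9.0 g/dL. Protocol Attachment 3 scores hemoglobin as low at "Males: ≤ 13 g/dL Females: ≤ 11.5 g/dL".

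**The concern.** An endpoint defined as change needs an analysis that compares post-treatment values with pre-treatment values. A table of out-of-range values by arm does not do that. It mixes patients who were abnormal on arrival with patients who became abnormal on treatment.

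The analytes affected are ones of interest for this drug. In the Phase 1 combination cohort (protocol Table 9.5-3), anemia was reported in 13 of 19 patients, creatinine increase in 7 of 19 and AST increase in 4 of 19. On monotherapy (Table 9.5-1), ALT increase was reported in 17.0%. Eligibility allows abnormal entry values for all four. If the laboratory tables cannot separate entry status from worsening, they are hard to read on exactly these tests.

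**Working it through.** **Plan's own figure.** The documents state no figure for laboratory data, so there is none to reproduce. The arm sizes of 42 and 21 come from protocol 14.5.

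**Endpoint against rule, one hypothetical patient.** A patient enters with ALT 2.0 x ULN and creatinine 1.6 x ULN, both allowed, and neither value ever moves. The 6.1.3 endpoint (change) is zero. A plain out-of-range summary shows two abnormal tests.

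**Effect on an arm difference.** Assumptions, none of them in the documents:
- 8.6.3 is implemented as a count of patients ever out of range on a test.
- A share b of patients is out of range at entry, equally in both arms, and is counted.
- Among patients normal at entry, new abnormality occurs in p0 = 20% on PboE and p1 = 40% on CBE.

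Proportion ever out of range in an arm = b + (1-b)p. Arm difference = (1-b)(p1-p0).

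SD of chance imbalance in b between arms = sqrt(b(1-b)(1/42 + 1/21)).

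| b | PboE | CBE | Difference (points) | Ratio | SD of imbalance in b (points) |
|---|---|---|---|---|---|
| 0 (new abnormality only) | 20% | 40% | 20 | 2.00 | – |
| 0.1 | 28% | 46% | 18 | 1.64 | 8.0 |
| 0.2 | 36% | 52% | 16 | 1.44 | 10.7 |
| 0.4 | 52% | 64% | 12 | 1.23 | 13.1 |
| 0.6 | 68% | 76% | 8 | 1.12 | 13.1 |

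With p0 = 30% and p1 = 50% the differences are the same, and the ratio falls from 1.67 at b = 0 to 1.11 at b = 0.6.

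**Effect of imbalance.** Take b = 0.4 overall and an imbalance of 13 points (about one SD), keeping the pooled share at 0.4.
- More entry abnormality on PboE (b = 0.357 CBE, 0.487 PboE): CBE 0.357 + 0.643 x 0.40 = 61.4%; PboE 0.487 + 0.513 x 0.20 = 58.9%. Difference about 2.5 points.
- More on CBE (b = 0.443 CBE, 0.313 PboE): CBE 0.443 + 0.557 x 0.40 = 66.6%; PboE 0.313 + 0.687 x 0.20 = 45.1%. Difference about 21.5 points.
- At 26 points (about two SDs) with more on PboE (b = 0.313 CBE, 0.573 PboE): 58.8% against 65.9%, so the difference reverses to about -7 points.

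The SD formula ignores stratification. Low hemoglobin by the Attachment 3 cut-offs puts a patient in the intermediate/poor group, which is a stratification level. Imbalance in low hemoglobin should therefore be smaller than the formula gives. No such restraint applies to creatinine, transaminases, bilirubin or triglycerides.

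**The case against.** The strongest reply is that 8.6.3 is silent rather than wrong. A reader might infer that the SAP counts entry abnormalities as on-study toxicity. It does not say so: it defines no patient-level ever-abnormal count and does not call out-of-range values toxicity. A programmer who read 6.1.3 with the 8.3 baseline could produce a sound table. That stands against the strong reading. It does not close the gap, because 8.6.3 invokes no baseline and 8.6.4 uses its own (the Cycle 1 Day 1 pre-dose measurement), so both the baseline and the counting rule are left to programming.

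Second, the main safety comparison rests on adverse events, and those are already relative to baseline. Protocol 15.1 sends treatment-emergent, clinically significant laboratory results to the adverse event page. This stands and limits the point. What remains is laboratory worsening without symptoms and without a change in study drug or concomitant therapy. That worsening need not be recorded as an adverse event, so the laboratory tables may be the only place it appears.

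Third, a grade table still shows a patient who moves from a low to a higher grade. This also stands. The weakness lies mainly in out-of-range counts and low grades.

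Fourth, the inputs are assumed. This stands in full. It is tempting to use the Phase 1 creatinine figure (7 of 19) as a new-onset rate, but it is an adverse event rate in all treated patients, whatever their entry value. Likewise, the Attachment 3 hemoglobin cut-offs are prognostic limits, not laboratory normal ranges, so they do not give an entry prevalence.

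**Conclusion.** The point holds in a limited form. The laboratory part of the 6.1.3 endpoint has no matching analysis, and nothing in 8.6.3 keeps abnormalities allowed at entry apart from new ones.

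Under balance, the arm difference in an ever-out-of-range count is multiplied by (1-b). Over the assumed range of b from 0.1 to 0.6, a 20-point difference becomes 18 to 8 points. The documents do not give b, so no single value can be defended.

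A reader might also infer that a real difference will be diluted. The documents do not support that as a prediction: dilution is the expected direction only if entry abnormality is balanced, and in 63 patients imbalance can inflate or reverse the difference.

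No laboratory hypothesis test is planned, so no error rate, power figure or decision rule is affected. The change is worth making because the better analysis uses data already scheduled.

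**What to change.** Amend SAP 8.6.3 to use the SAP 8.3 baseline. For chemistry and hematology tests with scheduled post-baseline collection, present:

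- change from baseline by visit;
- shift tables of baseline CTCAE grade (or normal-range category where no grade exists) against the worst value after first dose;
- the number of patients by arm whose worst value after first dose is worse than baseline, among those with a baseline and at least one post-baseline value.

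Tests scheduled only at screening (urinalysis, HbA1c, coagulation, total cholesterol) should be summarized at baseline, with any later results listed. Triglycerides have one scheduled repeat, at Cycle 2, and can be shown for that visit. While the section is open, use one CTCAE version: it appears as 4.0 in 6.1.3, 4.03 in 8.6.2 and 4.3 in 8.6.3.

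The cost is a paragraph of SAP text and one extra set of tables. No new data are needed, since chemistry and hematology are already scheduled at screening, Cycle 1 Day 1 and later visits. The small downside is that patients without a baseline or a post-baseline value leave the denominator, so their number should be shown by arm.

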### **8.6.4 Vital Signs**

Changes in selected vital signs will be summarized by treatment arm and by change over time, which includes change from baseline at each visit where parameters are scheduled to be collected. Baseline is defined as the measurement obtained on Cycle 1, Day 1 before the first dose of study drug is administered.

## **8.7 Missing Data**

See Section 7.5 for methods for handling missing data for primary and secondary endpoints.

## **8.8 Unblinding**

As directed by Calithera, Precision and Calithera will be unblinded at the time of the PFS primary analysis when approximately 48 events (PD or death) have occurred in the ITT population, prior to final database lock.

## 10 APPENDIX A: PROTOCOL SYNOPSIS

**Name of Sponsor:**

Calithera Biosciences, Inc.

**Name of Investigational Product:**

CB-839/placebo and everolimus

**Title of Study:**

A Randomized, Double-Blind, Placebo-Controlled Phase 2 Study Comparing CB-839 in Combination with Everolimus (CBE) vs. Placebo with Everolimus (PboE) in Patients with Advanced or Metastatic Renal Cell Carcinoma (RCC)

**Protocol Number:** CX-839-005

**Study Centers:**

Multicenter: Unites States and Europe

**Study period (years):**

Estimated 35 months including enrollment and follow-up

**Phase of development:**

Phase 2

**Objectives:**

***Primary Objective***

The primary objective is to compare the progression free survival (PFS) per Response Evaluation Criteria in Solid Tumors (RECIST) v1.1 of patients treated with CB-839 + everolimus (CBE) versus placebo + everolimus (PboE) for advanced or metastatic clear cell RCC (ccRCC) previously treated with:

- At least 2 lines of therapy, including at least one vascular endothelial growth factor receptor (VEGFR) tyrosine kinase inhibitor (TKI)
- Radiographic progression of mRCC must have occurred (per investigator assessment) on or after the most recent systemic therapy and within 6 months prior to C1D1.

***Secondary Objective***

The secondary objective is to compare the overall survival (OS) of study patients treated with CBE vs. PboE.

***Additional Objectives***

The additional objectives are to:

- To compare the objective response rate (ORR), Duration of Response (DOR), and Disease Control Rate (DCR) of CBE vs. PboE
- To compare the safety and tolerability of CBE vs. PboE
- To investigate the population pharmacokinetics (PK) of CB-839

- To investigate the relationship of genetic variants and response to CBE vs. PboE
- Change in kidney-cancer related symptoms
- Change in mobility, self-care, usual activities, pain/discomfort, and anxiety/depression, and global health

**Study Design:**

Protocol CX-839-005 is a randomized, Phase 2, multicenter, double-blind, placebo-controlled study designed to evaluate the safety and efficacy of CBE compared with PboE in patients with advanced or mRCC. Figure 1: Study Design Schema Figure 1 illustrates the study design.

Patients eligible after completing all screening evaluations will be randomly assigned in a 2:1 ratio to receive one of the following treatments:

- CBE - The glutaminase inhibitor CB-839 [4 x 200 mg tablets (800 mg) twice daily (BID)] and the mTOR inhibitor everolimus [10 mg once daily (QD)]
- PboE - Placebo tablets [4 tablets BID] and everolimus [10 mg QD]

Randomization will be stratified by the following factors:

- Number of prior VEGFR-targeting TKI therapies: 1 vs. >1
- Memorial Sloan-Kettering Cancer Center (MSKCC) prognostic criteria for previously treated patients with mRCC: favorable vs. intermediate/poor risk

Treatment administrations are per the instructions and schedule of events outlined in the protocol. Crossover between treatment arms will not be allowed.

## 11 APPENDIX B: SCHEDULE OF STUDY ASSESSMENTS

(1 cycle = 28 days) Visit	Pre-randomization	Post-randomization				
	Screening 	Cycle 1		Cycle 2+	Cycle 13+ (Every 3 cycles) 	End of Treatment/ Follow up
	≤21 days prior to C1D1	Day 1  (≤3 days post randomization)	Day 15 (± 2 days)	Day 1 (± 5 days)	Day 1 (± 7 days)	EOT: Within 28 days post treatment discontinuation
Written Informed Consent	X					
Inclusion/Exclusion Criteria	X					
Demographics and Medical History	X					
Physical Examination 	X	X	X	X	X	X
Height	X					
Weight	X	X	X	X	X	X
Vital Signs 	X	X	X	X	X	X
Karnofsky Performance Status	X	X		X	X	X
12-lead ECG with QTcF	X					
Urinalysis 	X					
HbA1c levels 	X					
Triglyceride and total cholesterol levels 	X			X		
Coagulation tests 	X					
Serum Chemistry levels	X	X	X	X	X	X
Hematology	X	X	X	X	X	X
Serum or Urine Pregnancy Test 	X					X
Pharmacokinetic (PK) Assay 			X	X		
CB-839 or Placebo Dosing		CB-839 or Placebo will be administered twice daily (BID) with food				
Everolimus Dosing		Everolimus will be administered once daily (QD) at the same time every day				
Optional Tumor Biopsy		Can be collected any time on study. Patients must sign the optional tumor biopsy consent				
Archival Tumor Collection	X					
Radiographic Evaluation of Tumor Burden (diagnostic CT with intravenous contrast or MRI) 	X 			Every 8 weeks	Every 12 weeks	X
Quality of Life Questionnaires		X		X	X	X
Adverse Events						
Concomitant Medications	Document new or worsening AEs from time of first dose through 28 days after study treatment discontinuation. AE information will be collected at study visits and may also be collected via any other forms of communication or by subject report. Certain AEs and SAEs that are ongoing 28 days after study discontinuation are to be followed until resolution or determination by the investigator that the event is stable or irreversible.					
Follow up						X 
